6.3.1 Inclusion Criteria

Subjects must meet all of the following inclusion criteria:

- 1) Male or female;
- 2) Subjects aged 18 years or older (at the time of diagnosis of moderate to severe UC or CD);
- 3) Diagnosis of moderate to severe CD or UC for at least 6 months prior to Day 1 appointment according the clinical or endoscopic criteria (23, 24, 25, 26, 27);
- 4) Subjects who provided the written informed consent.

In addition, for the prospective period, eligible patients should present at least one of the following criteria that will only be applied at Day 1:

- For CD patients:
 - HBI \geq 8 or
 - CDAI \geq 220 or

Considering that for CD patients, the disease activity may not be clearly documented only with clinical data, some objective criteria may be considered as entry criteria for the 12-month prospective period:

- colonoscopy in the previous year suggestive of inadequate control of activity
or
- calprotectin levels in the previous year suggestive of inadequate control of activity (i.e. calprotectin >200ug/g) (28).

For UC: partial Mayo Score ≥5

Note 1: UC patients with no or mild disease activity at Day 1 will not continue to follow up. CD patient with no or mild disease activity at Day 1 but with colonoscopy or calprotectin levels (i.e. calprotectin >200ug/g) in the previous year suggestive of inadequate control of activity will progress to 12-month follow up.

Patients that fulfill the above criteria (active disease) will be followed for 12 months, in order to explore patterns of care.

Note 2: Patients with colostomy and prospective period:

Although clinical scales defined above are impacted by colostomy these patients will not be excluded from the protocol to ensure the assessment of different clinical presentations of the IBD. In addition, patients with colostomy must follow the same criteria as above to be eligible to the prospective phase.

Note 3: Patients who are eligible for the prospective period, it means, with active disease at Day 1 but who during the 12 months period presents disease remission and/or no activity disease condition, must continue in the study.

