10.1.2 Statistical analyses overview

Descriptive statistics will be calculated for all variables, including mean, median, standard deviation and range for numerical variables and absolute and relative frequencies for categorical variables. Whenever relevant, 95% confidence intervals (CI) will be computed. For each study endpoint, data will be summarized by IBD type (CD and UC).

Cross-sectional analysis

The cross-sectional analysis will be conducted once all patients have completed the Day 1 assessment (expected to occur 6 months after start of enrolment).

This analysis will allow a characterization of the study population, the estimation of primary endpoints and to compare the subgroup of patients with no or light activity of disease and those with moderate to severe activity. Hence, for each IBD type, the patients with disease activity will be compared with patients with no or light activity regarding socio-demographic, clinical and treatment variables of interest. Chi-square or Fisher exact tests will be used to compare activity vs non-activity regarding qualitative variables and t-student / Mann-Whitney tests will be used for comparison of quantitative variables. If applicable, logistic regression will be used for evaluating associated variables. All tests will be two-sided considering a significance level of 5%.

Longitudinal analysis

The longitudinal analysis will be performed once all the patients that were included in the prospective period have completed the 12-month follow up.

The proportion of controlled patients will be presented as well as the 95%CI at the 12-month follow up assessment. If applicable, logistic regression will be used for calculating odd ratios and 95% confidence intervals for the patient control at month 12 determined by independent variables. All tests will be two-sided considering a significance level of 5%.

In case the expected ratio of IBDs (50%CD/50%UC) is not attained at 2 and 4 months of enrolment, the participating sites will be instructed to change future enrolments so that this balance is achieved and that at least 30 UC patients and 30 CD patients with active disease enter the prospective follow-up.

For details of the statistical analyses please refer to the Statistical Analysis Plan.

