- Health resources (previous 3 years) will be described by IBD group and by disease activity, for the following events: drug therapies, number and type of imaging and laboratory testing, surgeries, number, reason and duration of hospitalizations, number and type of consultations with gastroenterologists or other medical specialists and adverse events.
- Health Care Resource Costs
Costs will be reported in total and on a per patient per month basis. Costs will be obtained by multiplying resource use with relevant unit costs. Unit costs for resource items will be collected by in Brazilian reliable administrative databases or other sources.

UC or CD-related health care costs. Consumer price index (CPI)-adjusted IBD-related health care costs will be computed as total costs, medical costs, drug costs, and other costs.

Treatment pattern costs. Treatment pattern costs will be calculated as total UC or CD-related health care costs, stratified by the defined treatment patterns.

In addition to the descriptive cost data, multivariate cost models may be developed where the observation time is divided into intervals of equal length.

For patients with active IBD at study appointment (Day 1), and included in the prospective period, the following analysis will be conducted:

- Descriptive statistics will be presented in a summary table, for the main socio-demographics, clinical characteristics and treatment regimen of the included patients at Day 1 (baseline), by IBD disease.
- The proportion of patients with active CD after 12 months among patients who had moderately to severely active CD at Day 1 (baseline) will be expressed as percentage and determined as

$$\frac{CD \text{ patients with } HBI \geq 8 \text{ or } CDAI > 220 \text{ after 12 months}}{Total \text{ CD patients with } HBI \geq 8 \text{ or } CDAI > 220 \text{ at Day 1}} \times 100$$

- Similarly, the proportion of patients with active UC after 12 months among those who had moderately to severely active UC at Day 1 (baseline) will be expressed as percentage and determined as:

$$\frac{UC \text{ patients with partial Mayo score } \geq 5 \text{ after 12 months}}{Total \text{ UC patients with partial Mayo score } \geq 5 \text{ at Day 1}} \times 100$$

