- Patients that had light or no activity of disease at the end of the 12-month follow-up will be compared with patients that remained with active disease, regarding socio-demographic, clinical and treatment variables of interest. Similarly to the cross-sectional analysis, the comparison of categorical variables will be conducted with Chi-square or Fisher exact tests and t-student or Mann-Whitney tests will be used to compare quantitative variables.
- If applicable, variables associated with having light or no activity 12 months after baseline will be identified through logistic regression models for each IBD disease and OR (95%CI) will be presented.

- In addition, survival analysis with Kaplan Meier curves and Cox regression models will be used (if applicable) to identify factors associated with achieving light or no activity with baseline treatment (continued or initiated at baseline), during follow-up. In this analysis, patients that remained with active disease or that change treatment due to lack of disease control will be censored and, conversely, success will be defined as having light or no active disease. Time to success will be considered as dependent variable in survival analysis methods.
- The number and reason for treatment changes during follow-up will be summarized and treatment patterns during prospective period will also be described. Patients with treatment changes will be compared with those without changes, regarding main socio-demographic, clinical and treatment baseline variables. The comparison of categorical variables will be conducted with Chi-square or Fisher exact tests and t-student or Mann-Whitney tests will be used to compare quantitative variables.
- If applicable, Poisson regression models based on generalized linear equations will be used to examine the relationship between variables of interest and the incidence of the treatment changes during follow-up.

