## **7 STATISTICAL ANALYSIS**

### **7.1 General considerations**

As the study is an observational study, epidemiologic methods will be performed in the data analysis. A descriptive analysis will be obtained for all relevant variables, with absolute and relative frequency for categorical variables and mean, standard variation, median, maximum and minimum (or range) for continuous ones. For each study endpoint, data will be summarized by IBD type (CD or UC). The variable normality assumption will be tested using the Kolmogorov-Smirnov test. Non-parametric tests will be used whenever the assumptions for parametric tests are not accepted. Statistical tests will be performed considering bilateral tests and a significance level of 0.05.

All statistical analyses will be performed using the statistical software SAS® (version 9.4; SAS Institute Inc., Cary, USA).

The statistical analysis of the study include a cross-sectional analysis (at the end of the cross-sectional study) and a longitudinal analysis (at the end of the 12-month follow-up period). No interim analyses are planned.

- Cross-sectional analysis: it is expected to obtain a characterization of the study population, the estimation of primary endpoints and the comparison of the subgroups of patients with no or mild activity of disease and those with moderate to severe activity. Hence, for each IBD type, the patients with disease activity will be compared with patients with no or mild activity regarding socio-demographic, clinical and treatment variables of interest. Further details of this analysis are described in Section 7.5 and 7.6.
- Longitudinal analysis will be calculated the proportion of controlled patients after 12-month follow up assessment, as well if applicable, logistic regression will be used for calculating odd ratios and 95% confidence intervals for the patient control at month 12 determined by independent variables. Further details of this analysis are described in Sections 7.5 and 7.6.

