## 7.2 Analysis Sets

In this study, they will be analyzed two populations:

- The cross-sectional population will include all patients who have completed the Day 1 assessment (expected to occur 6 months after start of enrolment).
- The longitudinal population will include all patients included in the prospective period (patients with active IBD in Day 1).

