  - For quantitative variables, the assessment of a significant difference between groups will be made through the t-test for independent samples or Mann-Whitney test in case of non-normality of the quantitative variable distribution;
  - If applicable, for patients with CD and UC, the assessment of independent variables which can be associated with the disease control (no or mild activity) after 12 months

follow-up will be performed using a logistic regression model. The ORs estimates and the respective 95% confidence intervals will be presented.

- If applicable, a survival analysis, with Kaplan Meier curves and Cox regression models to identify factors associated with the time of achieving mild or no activity with baseline treatment (continued or initiated at baseline) (dependent variable) will be performed for each type of IBD. The event of interest will be: have mild activity or no active disease. Thus, patients who remained with active disease or who change treatment due to lack of disease control will be censored and, conversely, success will be defined as having mild or no active disease. The survival analysis will include:
  - A non-parametric estimation of the survival function using the Kaplan-Meier estimator (global and stratified by categories for each categorical variable).
  - A comparison of estimated survival function curves of the different categories in each variable using the Log-Rank non-parametric test.
  - If applicable, the semi-parametric Cox proportional hazards model will be adjusted to identify potential factors associated with the time of achieving mild or no activity with baseline treatment (continued or initiated at baseline). The hazard ratios (HR) estimates and the respective 95% confidence intervals will be presented.
- A descriptive statistical analysis will be performed for the number and reason for treatment changes, as well for treatment patterns during the 12 month follow-up period by IBD type (CD and UC);
- For each type of IBD (CD or UC), a comparison of patients with treatment changes with those without changes 12 month follow-up, regarding main socio-demographic, clinical and treatment-related variables (at baseline) will be performed
  - For qualitative variables, the assessment of a significant difference between groups will be done using the Chi-Square Test or the Fisher's Exact Test depending if the assumption of cell frequency to be made;

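### The 12-month formulas in protocol 10.3 divide patients scored active at month 12 by all patients active at Day 1, so a patient without a month-12 score counts as not active

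*Protocol*

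**What the plan says.** Protocol 10.3 introduces the UC estimate as "the proportion of patients with active UC after 12 months among those who had moderately to severely active UC at Day 1 (baseline") and the CD estimate as "The proportion of patients with active CD after 12 months among patients who had moderately to severely active CD at Day 1 (baseline"). Each displayed formula has a numerator that needs a qualifying activity score after 12 months. Each denominator is the total number of patients who met the activity threshold at Day 1. The sentence above the block limits it to patients active at Day 1 who were included in the prospective period. That requires entry, not completion.

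The rest of the plan on this point:

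- **Entry to follow-up (protocol 6.3.1, Note 1).** UC patients who are not active at Day 1 are not followed. A "CD patient with no or mild disease activity at Day 1 but with colonoscopy or calprotectin levels" suggestive of inadequate control is followed.
- **Analysis set (SAP 7.2).** "The longitudinal population will include all patients included in the prospective period (patients with active IBD in Day 1"). A month-12 score is not required.
- **Leaving early (protocol 6.3.3).** Withdrawal of consent, loss to follow-up and death are among the listed reasons for ending before month 12.
- **Missing data.** Protocol 10.5 rules out imputation except for the patient-reported tools. SAP 7.7 replaces no missing values.
- **Controlled proportion.** Protocol 10.1.2: "The proportion of controlled patients will be presented as well as the 95%CI at the 12-month follow up assessment". SAP 7.1 says much the same: "Longitudinal analysis will be calculated the proportion of controlled patients after 12-month follow up assessment". Neither gives a denominator. SAP 7.6 equates control with no or mild activity.
- **Sensitivity analysis (SAP section 8, item 7).** The active proportion is repeated with scores from specialist appointments in a 30-day window.

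The SAP's own 12-month formulas in 7.6 are redacted, and its table shells are not in the text available for review.

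**The concern.** The numerator needs a month-12 score and the denominator does not. A patient active at Day 1 who has no month-12 score therefore stays in the denominator and can never enter the numerator. That is arithmetically the same as recording the patient as not active, which is the favourable direction for an estimate of persisting disease activity.

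At stake is the plan's 12-month answer for patients with active disease at Day 1. The more patients go unscored, the lower the reported activity. If the controlled proportion is then read as the complement, patients who were lost or who died are reported as controlled. The same section also compares patients with light or no activity "at the end of the 12-month follow-up will be compared with patients that remained with active disease". Both of those groups need a score, so the comparison and the proportion would rest on different numbers of patients without the plan saying so.

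**Working it through.** **Inputs from the documents.** The formulas and lead-ins are in protocol 10.3, the entry rules in 6.3.1, the scoring times (Day 1 and month 12) in 7.1 and 7.2, and the reasons for leaving in 6.3.3. The only stated figure for the size of these denominators is in 10.6: 40-60 CD and 30-50 UC patients. From 400 patients, a 50/50 split and 20-30% active, 400 × 0.5 × 0.2 = 40 and 400 × 0.5 × 0.3 = 60. This reproduces the CD range but not the UC range. That mismatch is a separate matter; the figures serve here only for scale.

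**Assumed inputs.** The documents give no drop-out rate and no 12-month activity rate. Let *a* be the active rate among scored patients, *d* the unscored fraction, and *r* the active rate among the unscored.

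**Step 1: the identity.** Let D patients be active at Day 1, m of them unscored at month 12, and x scored active. The printed ratio is x/D = (x + 0·m)/((D − m) + m), which sets all m unscored patients to not active. With a = x/(D − m) and d = m/D:

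- printed result = a(1 − d), the lower bound
- upper bound, all unscored active = a(1 − d) + d

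For UC this is exact, because only patients active at Day 1 are followed and the numerator lies inside the denominator. For CD it holds once the numerator is limited, as the lead-in says, to patients active at Day 1.

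**Step 2: size, with a = 50%.**

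| Unscored | Printed | Scored-only | Upper bound |
|---|---|---|---|
| 10% | 45% | 50% | 55% |
| 20% | 40% | 50% | 60% |
| 30% | 35% | 50% | 65% |

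In patients, with D = 40 and 8 unscored: 16/40 = 40% printed, 16/32 = 50% scored-only, (16 + 8)/40 = 60% upper bound. Read as a complement, the controlled proportion is 100 − 40 = 60%, against 50% among those scored.

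**Step 3: is scored-only always better?** No. Leaving deaths aside, since a patient who died has no month-12 activity state, the full-cohort value is a(1 − d) + d·r. The printed error is −d·r and the scored-only error is d(a − r). The two are equal in size at r = a/2. With a = 50% and d = 20%:

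| r | Printed error | Scored-only error |
|---|---|---|
| 10% | −2 points | +8 points |
| 25% | −5 points | +5 points |
| 50% | −10 points | 0 |
| 70% | −14 points | −4 points |

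Only the bounds hold whatever the reason for the missing score.

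**Step 4: the interval.** The plan names no interval method, so Wilson 95% intervals are used here, with 50 active at Day 1 and 10 unscored:

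| Scored active | Printed (width) | Scored-only (width) |
|---|---|---|
| 20 | 20/50: 27.6-53.8 (26.2) | 20/40: 35.2-64.8 (29.6) |
| 30 | 30/50 (26.2) | 30/40 (26.0) |
| 36 | 36/50 (24.2) | 36/40 (19.1) |

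The printed interval uses an N that includes patients with no outcome. Whether it is narrower or wider than the scored-only interval depends on the activity rate.

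**The case against.** The strongest reply is that the operative text cannot be seen. Protocol section 10 describes the analyses as foreseen at planning and defers detail to the SAP, whose formulas are redacted. This stands as a limit on reach: the point concerns the protocol's formulas and shows nothing about the analysis actually run.

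A second reply is that a rule against imputing missing values implies dropping unscored patients. An analyst could read it that way. But neither protocol 10.5 nor SAP 7.7 says that a patient leaves this denominator, and the printed denominator is a Day 1 total. If dropping was intended, the formula says something else.

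Third, the 30-day-window analysis in SAP section 8 and the disposition reporting in SAP 7.3 may seem to cover the gap. The window may change how many patients are unscored, but it does not say how to treat those who remain so. Disposition counts discontinuations; it does not fix a denominator, and a patient who completes may still lack a score.

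Three stronger readings are tempting but not supported:

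- **That the printed interval is always too narrow.** The widths above show that it can be wider.
- **That CD patients who entered by colonoscopy or calprotectin inflate the CD proportion.** The displayed CD numerator does not repeat the Day 1 condition, but its lead-in sentence does. The reading requires setting that sentence aside.
- **That the controlled proportion is defined as the complement.** It is not. SAP 7.6 describes control as "which can be associated with the disease control (no or mild activity) after 12 months" of follow-up, which points to a scored state. The consequence for lost and dead patients follows only if the complement is used.

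**Conclusion.** The point holds for the formulas printed in protocol 10.3. Followed literally, the UC result equals the scored-only rate times (1 − unscored fraction), the lowest value compatible with the data. The CD result does the same under its lead-in. With 20% unscored and 50% active among those scored, the shortfall against scored-only is 10 points, within a 20-point range of 40% to 60%. Both rates are assumptions.

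A reader might infer that scored-only is the correct answer, or that the Day 1 results are affected. Neither follows. Scored-only is further from the full-cohort value when fewer than half as many of the unscored are active as of the scored. The primary endpoints are measured at Day 1 and do not use these formulas. The point is worth fixing because the printed rule moves a key secondary estimate in the favourable direction, the expected groups are small, and the correction is cheap.

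**What to change.** 1. For both the active and the controlled proportion, state that the denominator is patients active by score at Day 1 (HBI or CDAI for CD, partial Mayo for UC) who have a month-12 score. Repeat the Day 1 restriction in the CD numerator. The two proportions then sum to 100%. If the redacted SAP formulas already do this, align the protocol with them.
2. Next to each proportion, print the number unscored by IBD type, with deaths shown separately.
3. Because scored-only can also be biased, add two bounding rows over all patients active at Day 1: all unscored active, and all unscored not active. Apply the same rule to the 30-day-window sensitivity analysis.

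The cost is one denominator sentence, a few table rows and a wider stated range. No new data are needed.

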10.4 Interim Analyses

No interim analyses are planned for this study. The planned analyses will be conducted in two moments, at the end of the cross-sectional study and at the end of the 12-month follow-up period.

10.5 Handling of missing data

Given that all analyses are descriptive in nature, no imputation of missing data will be performed, except when detailed in the SAP regarding the PRO tools.

10.6 Determination of Sample Size

It is expected to include approximately 400 patients regardless of IBD type. This sample size will allow estimates with 95% confidence interval and a margin of error less than 5%.

Based on the above and considering an expected ratio of CD/UC of approximately 50%/50%, and that the rate of inadequate control of disease activity varies from 20-30% (regardless of the IBD type), it is expected to analyze 40-60 patients with CD and 30-50 patients with UC during the 12-month follow up.

11 Reports

A Non-Interventional Study Report based on the results obtained will be prepared and submitted to Global Research for distribution. The Final Study Report should be available within one year from collection of the last data point, and the participating sites should be informed about the results when the report is finalized.

12 Publications

Takeda aims to have the results of this study published.

Takeda has the right to use the data and results for regulatory purposes and for internal presentation within the company and to partners.

13 Archiving of Study Documentation

During the course of the study the Site Responsible must as a minimum file the essential documents (Section 4.4), the protocol, any amendments, the list of participating subjects, the written informed consents, the CRFs and the progress reports in the Study Site File. After final database lock the Site Responsible must as a minimum store the list of participating subjects and the signed Informed Consent Forms on site for 5 years. The Site Responsible should store additional study documentation for a longer period of time as required by any local regulations and/or hospital requirement.

14 References

